9.4.4 Study design for Study Objective 1.2.4 (Neurocognitive Outcomes)

The primary objective of this study is to use CogState testing to evaluate change in neurocognitive function from end of Induction to 2 years off therapy. The three secondary objectives include first, use of parent-reporting on the BRIEF questionnaire to assess change in neurocognitive function from end of Induction to 2 years off therapy, and for the other secondary aims, use of a psychologist administered battery to assess change in neurocognitive function from end of therapy to 4 years off therapy.

Actual CogState scores for each domain at each time point will be summarized and examined by descriptive statistics and scatter plots. Change in score for a domain from end of Induction will be calculated and similarly summarized by descriptive statistics. For the CogState scores, the mean change of score from end of Induction to a later time point will be estimated along with its 95% CI. One sample t-test on the change of score will be used to examine if there is significant decline in neurocognitive function from end of Induction to 2 years off therapy. Thus our analysis of CogState outcome data will be restricted to participants who have completed CogState testing following Induction (i.e., we will include data from patients who are 5 years of age or older by Day 1 of Consolidation Cycle 1). Outcomes for younger patients not completing the initial Induction assessment will be reported in a descriptive manner. Linear mixed models using scores from all time points as outcome will also be used to estimate the change in scores between time points with adjustment for within-patient correlation of the score by random effects for individual patients. If the change in score over time appears approximately linear in time, linear mixed models assuming time as a continuous covariate will be used to estimate the rate of decline over time and determine whether the rate of decline is significantly higher than zero.

Since each domain will be analyzed separately, the alpha level for each analysis is set to 0.01 for CogState and the psychologist administered battery and 0.017 for BRIEF according to Bonferroni adjustment to maintain an overall alpha of 0.05. For the primary objective utilizing CogState testing, assuming that there are 120 patients 5 - 18 years old who consent to participate in neurocognitive testing and receive all protocol therapy, there will be 80% power to detect the unit change

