provided in the table below in the mean change score between end of Induction and 2 years off therapy using a one-sample t-test at two-sided alpha level for the SD of the change of score between two time points provided in the table below. For the secondary objectives, mean change score will be compared from end of Induction to 2 years off therapy for the BRIEF and from end of therapy to 4 years off therapy for the psychologist administered battery, BASC-2 Anxiety, Depression, and Social Skills scores, and the PedsQL Total and Physical Health scores.

Outcome	Unit Change	Change SD
CogState (each of five tasks)	4.3	13.6
BRIEF (each of three tasks)	4.3	14.5
Estimated IQ	6.7	20.4
CVLT Total Score	4.3	13.6
Processing Speed Index	6.5	20.4
CMS Stories and Faces Immediate Memory	1.3	4.1
ABAS-II General Adaptive Composite	6.5	20.4
BASC-2 (each of three scales)	8.2	26.0
PedsQL (each of two scales)	10.3	32.4

In AAML0631, 91.7% of participants were between the ages of 5 and 18 and the upper age of enrollment was 21 years of age. Therefore, we would anticipate 91.7% or 138 of the 150 subjects in the proposed sample to be 5 - 18 years old. Based on the accrual to date to this optional embedded study, we project that up to 120 patients 5 - 18 years old will participate in neurocognitive testing and receive all protocol therapy.

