16.0 NEUROCOGNITIVE OUTCOMES IN PEDIATRIC APL TREATMENT

16.1 Study Design

The purpose of this optional embedded study is to longitudinally monitor cognitive side effects from this treatment, as defined by the following endpoints:

- Primary outcome:
 - To evaluate the change in CogState scores over time, defined as a decline of 5 units in mean scores apparent at 2 years off therapy, as measured by the five tasks of the computerized CogState battery (i.e., processing speed, visual attention, visual learning, working memory, executive functioning).
- Secondary outcomes:
 - To evaluate change in parent-reported executive functioning over time, defined as a decline of 5 units in mean scores apparent at 2 years off therapy, as measured by the Behavioral Regulation, Working Memory and Metacognition Indices of the parent-completed BRIEF.
 - To evaluate change in intellectual, memory, verbal learning, and adaptive functioning over time, defined by declines on the Wechsler-derived estimated IQ and Processing Speed scores, CMS Faces and Stories memory scores, CVLT Total score, and ABAS-II General Adaptive Behavior Composite score at 4 years off-therapy.
 - To evaluate change in parent-reported psychosocial functioning and quality of life over time, defined by declines on the BASC-2 Anxiety, Depression, and Social Skills scores, and the PedsQL Total and Physical Health scores at 4 years off-therapy.

For this study, we have chosen to maximize our ability to examine neurocognitive functioning across a wide age range with minimal institutional and participant burden. Towards this aim, a combination of computerized and traditional neurocognitive measures, using two batteries that are already widely used within COG member institutions will be utilized. Specifically, we will use a brief computerized assessment system (CogState; see below) that targets the neurocognitive processes known to be most affected in leukemia survivors (i.e., attention, processing speed, and memory), and a widely used rating scale (the BRIEF, see below) to evaluate real world behaviors related to these processes.⁷⁵ In addition, participants will also complete a short neurocognitive battery that has been used in COG ALTE07C1. Specifically, participants will complete a one hour screening battery of traditional neurocognitive tests, administered by a psychologist, evaluating intellectual functioning, immediate and learning memory, processing speed, and working memory.

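### The 0.01 level for the psychologist battery is 0.05/5, but section 16.1 names six cognitive and adaptive scores, so the Bonferroni bound for that objective is 0.06 unless the two CMS scores are one test

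*Combined protocol and SAP*

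**What the plan says.** Section 9.4.4 analyses each neurocognitive domain separately and states that "the alpha level for each analysis is set to 0.01 for CogState and the psychologist administered battery and 0.017 for BRIEF". The reason it gives is error control over the whole set of tests: these levels were fixed "according to Bonferroni adjustment to maintain an overall alpha of 0.05". It then gives a table of detectable mean changes. The tests are made "using a one-sample t-test at two-sided alpha level". The sample size is fixed by "assuming that there are 120 patients 5 - 18 years old who consent to participate in neurocognitive testing", and on that basis "there will be 80% power to detect the unit change" shown in each row.

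The outcomes are listed in section 16.1. The primary outcome is the five CogState tasks. There are three secondary outcomes:

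- three BRIEF indices;
- a cognitive and adaptive outcome made up of "Wechsler-derived estimated IQ and Processing Speed scores, CMS Faces and Stories memory scores, CVLT Total score, and ABAS-II General Adaptive Behavior Composite score";
- a psychosocial and quality-of-life outcome made up of three BASC-2 and two PedsQL scores.

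Section 9.4.4 says that the comparison from end of therapy to 4 years off therapy is made "for the psychologist administered battery, BASC-2 Anxiety, Depression, and Social Skills scores, and the PedsQL Total and Physical Health scores".

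**The concern.** The divisors fit the first two instruments: five CogState tasks give 0.05/5 = 0.01, and three BRIEF indices give 0.05/3, printed as 0.017. The battery takes the CogState level of 0.01, but section 16.1 names six cognitive and adaptive scores for it. If each is tested at 0.01, the stated Bonferroni guarantee of 0.05 does not follow.

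Section 9.4.4 also names no level for BASC-2 and PedsQL as such. It does not say whether they fall under the battery's 0.01 or whether the 0.05 is held per objective or across the battery.

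These scores address possible cognitive harm from arsenic in children. If the family is not declared beforehand, the threshold could be chosen after the results are seen.

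**Working it through.** **Inputs.** Per-test level 0.01 (battery and CogState) and 0.017 (BRIEF), overall 0.05, two-sided one-sample t-test, 80% power, and the unit changes and SDs: all from section 9.4.4. Score counts: section 16.1. The n of 120 is stated for the CogState objective; I assume that it applies to the other rows of the same table.

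**1. The plan's levels.** 0.05/5 = 0.0100 and 0.05/3 = 0.0167, rounded to 0.017. Both match the number of tests within one objective.

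**2. The plan's table.** The noncentrality is (unit change/SD) × √120. For CVLT it is (4.3/13.6) × 10.954 = 3.464. The two-sided critical value at 0.01 with 119 df is 2.618, and the noncentral t gives 79.9% power. All rows:

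| Row | Unit change / SD | Level | Power |
|---|---|---|---|
| CogState | 4.3 / 13.6 | 0.01 | 79.9% |
| BRIEF | 4.3 / 14.5 | 0.017 | 79.5% |
| Estimated IQ | 6.7 / 20.4 | 0.01 | 83.4% |
| CVLT | 4.3 / 13.6 | 0.01 | 79.9% |
| Processing Speed | 6.5 / 20.4 | 0.01 | 80.7% |
| CMS | 1.3 / 4.1 | 0.01 | 80.2% |
| ABAS-II | 6.5 / 20.4 | 0.01 | 80.7% |
| BASC-2 | 8.2 / 26.0 | 0.01 | 79.7% |
| PedsQL | 10.3 / 32.4 | 0.01 | 80.5% |

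The table therefore rests on n = 120 and 0.01 throughout, with 0.017 for BRIEF. The exception is Estimated IQ. With SD 20.4 the 80% detectable change is 6.45, printed as 6.5 for Processing Speed and ABAS-II but as 6.7 for IQ. The BASC-2 and PedsQL rows fit 0.01, although the text does not assign that level to them by name.

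**3. Family-wise error at 0.01 per test.** The Bonferroni bound is k × 0.01; under independence the error is 1 − 0.99^k.

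| k | Reading | Bound | Independent |
|---|---|---|---|
| 5 | CMS as one test; or BASC-2 and PedsQL alone | 0.050 | 0.049 |
| 6 | six scores named in section 16.1 | 0.060 | 0.0585 |
| 11 | six scores plus BASC-2 and PedsQL | 0.110 | 0.105 |

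**4. Effect of correlation.** Simulating six equicorrelated test statistics at 0.01 each gives an error of about 0.055, 0.048 and 0.039 for assumed correlations of 0.3, 0.5 and 0.7. The documents give no correlation, so these are illustrations.

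**5. Effect of using 0.05/6 = 0.0083 (n = 120).** Power at the printed changes is 78.1% for CVLT, 78.4% for CMS and 78.8% for Processing Speed and ABAS-II. It is 81.8% for IQ at 6.7. The 80% detectable change rises by about 2%: from 6.45 to 6.58 at SD 20.4, from 4.30 to 4.38 for CVLT, and from 1.30 to 1.32 for CMS.

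**The case against.** The strongest reply is that the plan tests five battery scores, not six. The table has five cognitive and adaptive rows because CMS Stories and Faces share one. Rows covering several scores are otherwise marked, as in "CogState (each of five tasks"); the CMS row is not. Five rows match 0.05/5. This reading remains open, but it is the weaker one. Section 16.1 refers to CMS scores in the plural, section 16.5.3 treats Faces as visual memory and Stories as verbal memory, section 9.4.4 analyses domains separately, and a composite is nowhere defined.

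Section 16.5.3 also uses the Vocabulary and Block Design subtests only at baseline to estimate IQ. Taken literally, IQ change could not be tested and the count would return to five even with CMS split. That conflicts with sections 9.4.4 and 16.1, which do plan an IQ change, so it is one more point to reconcile.

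A reader might go further and infer a family of eleven, with an error of up to 0.110, about twice the stated level. Section 9.4.4 assigns both remaining secondary aims to the battery, and section 16.1 and Appendix VI include the parent questionnaires in it, so that literal reading is possible. The documents do not establish it. Section 16.1 makes BASC-2 and PedsQL a separate outcome, section 9.4.4 lists them apart from the battery, and the plan's divisors of 5 and 3 count tests within an objective. On that rule 0.01 is exactly 0.05/5 for the five BASC-2 and PedsQL scores.

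Two further points stand. Bonferroni is a worst-case bound, so correlated scores could keep the true error below 0.05. And because the tests are two-sided, the bound on a false decline among six scores is 6 × 0.005 = 0.03.

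On Estimated IQ, 6.7 is conservative and n = 120 is not printed for that row specifically. At 0.01 it would fit an n of about 112 (80.2% power), but no such n is given, and the other two SD 20.4 rows fit 120.

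**Conclusion.** The point holds in a limited form. With six cognitive and adaptive scores tested at 0.01, the claimed Bonferroni guarantee fails for that objective: the bound is 0.060 (0.059 if independent) rather than 0.05. This rests on CMS Faces and Stories being separate tests and on IQ change being tested. It does not show that the true error exceeds 0.05, which depends on correlations not given in the documents. For BASC-2 and PedsQL the level is right on the per-objective reading, and only its statement is missing.

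The size is small: about 0.01 on the bound and about 2 points of power. Only secondary outcomes of an optional study under exploratory aim 1.2.4 are affected, and no primary endpoint is touched. The Estimated IQ row is a separate inconsistency that says nothing about multiplicity.

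**What to change.** In section 9.4.4:

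- State that the 0.05 is held within each objective.
- Use Holm's procedure at 0.05 within the six cognitive and adaptive scores (first step 0.05/6 = 0.0083) and, separately, within the five BASC-2 and PedsQL scores (first step 0.05/5 = 0.01). Holm keeps the same guarantee and is never less powerful than Bonferroni. If CMS Stories and Faces are meant as one composite, define it; the first family then has five tests and 0.01 stands.
- Restate the detectable changes for the six-score family at 0.0083, for example 6.58 for SD 20.4 and 4.38 for CVLT.
- Correct the Estimated IQ row so that it agrees with the other SD 20.4 rows, or state the different n behind it.
- Reconcile the planned test of IQ change with the baseline-only use of the IQ subtests in section 16.5.3.

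The cost is a few lines of text and slightly less favourable stated detectable changes. No added patients, visits or data are needed.

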9.5 Gender and Minority Accrual Estimates

The gender and minority distribution of the study population is expected to be:

Racial Categories	Ethnic Categories				Total
	Not Hispanic or Latino		Hispanic or Latino		
	Female	Male	Female	Male	
American Indian/ Alaska Native	0	3	0	0	3
Asian	5	0	0	0	5
Native Hawaiian or Other Pacific Islander	0	0	0	0	0
Black or African American	11	9	0	0	20
White	57	38	21	14	130
More Than One Race	0	0	0	0	0
Total	73	50	21	14	158

This distribution was derived from AAML0631.

10.0 EVALUATION CRITERIA

10.1 Common Terminology Criteria for Adverse Events (CTCAE)

This study will utilize version 4.0 of the CTCAE of the National Cancer Institute (NCI) for toxicity and performance reporting. A copy of the CTCAE version 4.0 can be downloaded from the CTEP website

(http://ctep.cancer.gov/protocolDevelopment/electronic_applications/ctc.htm).

Additionally, toxicities are to be reported on the appropriate case report forms.

Please note: 'CTCAE v4.0' is understood to represent the most current version of CTCAE v4.0 as referenced on the CTEP website (i.e., v4.02 and all subsequent iterations prior to version 5.0).

10.2 Response Criteria for Patients with Acute Promyelocytic Leukemia

10.2.1 Hematologic Complete Remission (hCR and hCRi)

- In a bone marrow sample, hematologic complete remission (hCR) is defined as a differential count of at least 200 nucleated cells with less than 5% promyeloblasts/abnormal promyelocytes. There must be signs of recovering marrow with an absolute neutrophil count $> 1,000/\mu\text{L}$ and platelets $> 100,000/\mu\text{L}$. Extramedullary disease must have resolved including clearance of the CNS (CSF negative for blasts) and resolution of chloromas.
- Hematologic complete remission with incomplete blood count recovery (hCRi): all the above criteria for hCR except for residual neutropenia ($< 1,000/\mu\text{L}$) or thrombocytopenia ($< 100,000/\mu\text{L}$).

Patients who appear not to have achieved hematological complete remission after Day 43 of Induction may benefit from consultation for a rapid pathology review (see [Section 13](#)).

10.2.2 Molecular Remission

- Molecular remission is the absence of PML-RAR α fusion transcript by RQ-PCR (with an assay sensitivity of at least 10^{-4}) in a bone marrow specimen obtained after at least 14 weeks of Consolidation therapy. A positive test (detectable PML-RAR α fusion transcripts) must be confirmed by a repeat test on a separate bone marrow specimen obtained at least 1 to 2 weeks later.

10.2.3 Treatment Failure/Events

- *Resistant Disease:* failure to achieve hCR/hCRi by Day 70 of Induction.
- *Molecular Resistant Disease:* persistence of PML-RAR α fusion transcript by RQ-PCR in two consecutive marrow samples taken 1 - 2 weeks apart following the MRD Positive Consolidation cycle (mitoxantrone/cytarabine/ATRA).

- *Induction Death:* all deaths during Induction phase prior to achievement of hCR/hCRi.

10.2.4 Relapse

- *Hematologic Relapse:* reappearance of promyeloblasts/abnormal promyelocytes (> 5%) in the bone marrow with genetic confirmation of t(15;17) PML/RAR α by cytogenetics, FISH or RQ-PCR in a patient who had previously achieved hCR/hCRi.
- *Molecular Relapse:* persistence of hematologic CR but reappearance of the PML-RAR α transcript by PCR testing in two successive bone marrow samples in a patient who had previously achieved molecular remission.
- *Extramedullary Relapse:* reappearance or development of promyeloblasts/abnormal promyelocytes found in the CSF or on biopsy of any tissue with features suspicious for extramedullary disease. Genetic confirmation of PML-RAR α with FISH or RT-PCR testing is required.

11.0 ADVERSE EVENT REPORTING REQUIREMENTS

11.1 Purpose

Adverse event data collection and reporting, which are required as part of every clinical trial, are done to ensure the safety of patients enrolled in the studies as well as those who will enroll in future studies using similar agents.

11.2 Determination of Reporting Requirements

Reporting requirements may include the following considerations: 1) the characteristics of the adverse event including the *grade* (severity); 2) the *relationship to the study therapy* (attribution); and 3) the *prior experience* (expectedness) of the adverse event.

Commercial agents are those agents not provided under an IND but obtained instead from a commercial source. In some cases an agent obtained commercially may be used for indications not included in the package label. In addition, NCI may on some occasions distribute commercial supplies for a trial. Even in these cases, the agent is still considered to be a commercial agent and the procedures described below should be followed.

Determine the prior experience Expected events are those that have been previously identified as resulting from administration of the agent. An adverse event is considered *unexpected*, for reporting purposes only, when either the type of event or the severity of the event is not listed in:

- *the current known toxicities for each commercial agent as provided in the Drug Information for Commercial Agents Used by the Children's Oncology Group posted on the COG website; or*
- *the drug package insert.*

Secondary Malignancy

A **secondary malignancy** is a cancer caused by treatment for a previous malignancy (e.g., treatment with investigational agent/intervention, radiation or chemotherapy). A metastasis of the initial neoplasm is not considered a secondary malignancy.

All secondary malignancies that occur following treatment need to be reported via CTEP-AERS. Three options are available to describe the event:

- Leukemia secondary to oncology chemotherapy
- Myelodysplastic syndrome
- Treatment related secondary malignancy

11.3 Reporting of Adverse Events for Commercial Agents – via CTEP-AERS

Expedited AE reporting must use CTEP-AERS (Adverse Event Expedited Reporting System), accessed via <https://eapps-ctep.nci.nih.gov/ctepaers>

Commercial reporting requirements are provided in Table B. The commercial agent(s) used in this study are listed in the front of this protocol immediately following the Study Committee roster.

- COG requires the CTEP-AERS report to be submitted within 7 calendar days of learning of the event.
- Use the NCI protocol number and the protocol-specific patient ID provided during trial registration on all reports.

CTCAE term (AE description) and grade: The descriptions and grading scales found in the revised NCI Common Terminology Criteria for Adverse Events (CTCAE) version 5.0 will be utilized for AE reporting. All appropriate treatment areas should have access to a copy of the CTCAE version 5.0. A copy of the CTCAE version 5.0 can be downloaded from the CTEP website at: http://ctep.cancer.gov/protocolDevelopment/electronic_applications/ctc.htm.

Table B

Reporting requirements for adverse events experienced by patients on study who have NOT received any doses of an investigational agent on this study.

CTEP-AERS Reporting Requirements for Adverse Events That Occur During Therapy With a Commercial Agent or Within 30 Days¹

Attribution	Grade 4		Grade 5
	Unexpected	Expected	
Unrelated or Unlikely			CTEP-AERS
Possible, Probable, Definite	CTEP-AERS		CTEP-AERS

¹This includes all deaths within 30 days of the last dose of treatment with a commercial agent, regardless of attribution. Any death that occurs more than 30 days after the last dose of treatment with a commercial agent that can be attributed (possibly, probably, or definitely) to the agent and is not due to cancer recurrence must be reported via CTEP-AERS.

11.4 Routine Adverse Event Reporting

Note: The guidelines below are for routine reporting of study specific adverse events on the COG case report forms and do not affect the requirements for CTEP-AERS reporting.

The NCI defines both routine and expedited AE reporting. Routine reporting is accomplished via the Adverse Event (AE) Case Report Form (CRF) within the study database. For this study, routine reporting while on protocol therapy will include all toxicities reported via CTEP-AERS and all Grade 3 and higher non-hematological Adverse Events and all grades of the following cardiac adverse events: prolonged QTc interval, ventricular arrhythmia, and left ventricular systolic dysfunction. Routine reporting while in follow-up (off protocol therapy) will include all toxicities reported via CTEP-AERS and all grades of the following cardiac adverse events: prolonged QTc interval, ventricular arrhythmia, and left ventricular systolic dysfunction.

NOTE: Adverse events related to coagulopathy including hemorrhage/bleeding and thrombosis/clotting events are NOT considered hematologic toxicities for this study. Coagulopathy in APL is a targeted event in this study and therefore it is important to report all Grade 3 or higher hemorrhage/bleeding and thrombosis/clotting events included in the CTCAE catalog as follows:

- Hemorrhage (all sites)
- Bleeding (all sites)
- Disseminated Intravascular Coagulation
- Hematosalpinx
- Menorrhagia
- Epistaxis
- Purpura
- Hematoma
- Vascular Access Complication (if related to thrombosis)
- Ischemia cerebrovascular
- Superior Vena Cava syndrome
- Thromboembolic event
- Superficial Thrombophlebitis
- Portal Vein Thrombosis

